8.4.6 Patient Diary

Patient diary cards will be provided to patients at the beginning of the Run-in-Period (Phase 1 only) and on Day 1 of every treatment cycle when rociletinib study drug is dispensed to the patient. Patients will use diary cards to note the date, time, and dose of rociletinib administration. At each clinic visit, patients will bring the diary with them to the clinic, along with the study drug bottle and any unused study drug, for study staff to review.

9 ADVERSE EVENT REPORTING

9.1 Definition of an Adverse Event (AE)

Patients will be monitored for AEs from the time the first dose of study drug is administered through 28 days after the last dose of study treatment. Study procedure-related AEs that occur after signing of the ICF and before administration of study drug will also be collected.

An AE is defined as any untoward medical occurrence in a patient administered a medicinal product that does not necessarily have a causal relationship with this treatment. An AE can, therefore, be any unfavorable and unintended sign (including an abnormal laboratory finding), symptom, or disease temporally associated with the use of an investigational product, whether or not related to the IMP. This includes an exacerbation of pre-existing conditions or events, intercurrent illnesses, drug interaction, or the significant worsening of the indication under investigation that is not recorded elsewhere on the eCRF under specific efficacy assessments. Anticipated fluctuations of pre-existing conditions, including the disease under study, that do not represent a clinically significant exacerbation or worsening are not considered AEs.

It is the responsibility of the Investigator to document all AEs that occur during the study. AEs should be elicited by asking the patient a non-leading question (eg, "Have you experienced any new or changed symptoms since we last asked/since your last visit?"). AEs will be reported on the AE eCRF. Symptoms reported spontaneously by the patient during the physical examination will also be documented on the AE eCRF (not on the physical examination eCRF, which is reserved for physical signs or findings).

9.2 Definition of a Serious Adverse Event (SAE)

An SAE is any untoward medical occurrence that occurs at any dose of rociletinib and MPDL3280A that:

- Results in death. Death may occur as a result of the underlying disease process. Nevertheless, any event resulting in death during the reporting period must be treated as an SAE and reported as such. All deaths occurring within 28 days of the last administration of rociletinib and/or MPDL3280A should be reported as SAEs;
- Is life-threatening (patient is at immediate risk of death from the event as it occurred);
- Requires in-patient hospitalization (formal admission to a hospital for medical reasons) or prolongation of existing hospitalization;
- Results in persistent or significant disability/incapacity;
- Results in a congenital anomaly/birth defect.

Important medical events that may not result in death, are not life-threatening, or do not require hospitalization may be considered SAEs when, based on appropriate medical judgment, they may jeopardize the patient and may require medical or surgical intervention to prevent one of the outcomes listed in this definition. Examples of such events include allergic bronchospasm

requiring intensive treatment in an emergency room or at home, blood dyscrasias or seizures that do not result in in-patient hospitalization, or the development of drug dependency or drug abuse.

9.3 Events or Outcomes Not Qualifying as SAEs

The following are not considered SAEs:

- Pre-planned or elective hospitalization including social and/or convenience situations (eg, respite care);
- Overdose of either rociletinib or MPDL3280A or concomitant medication unless the event meets SAE criteria (eg, hospitalization). However, the event should still be captured as a non-serious AE on the appropriate eCRF page;
- Events of progression of the patient's underlying cancer as well as events clearly related to progression of the patient's cancer (signs and symptoms of progression) should not be reported as a SAE unless the outcome is fatal during the study or within the safety reporting period. If the event has a fatal outcome during the study or within the safety reporting period, then the event of Progression of Disease must be recorded as an AE and as a SAE with CTC Grade 5 (fatal outcome) indicated;
- Diagnosis of progression of disease or hospitalization due to signs and symptoms of disease progression alone should not be reported as SAEs.

9.4 Clinical Laboratory Assessments as AEs and SAEs

It is the responsibility of the Investigator to assess the clinical significance of all abnormal values as defined by the list of reference ranges from the local laboratory. In some cases, significant changes in lab values within the normal range will require similar judgment.

An abnormal laboratory value that is not already associated with an AE is to be recorded as an AE only if any one of the following criteria is met:

- An action on the study drug is made as a result of the abnormality;
- Intervention for management of the abnormality is required;
- At the discretion of the Investigator should the abnormality be deemed clinically significant.

9.5 Pregnancy or Drug Exposure During Pregnancy

If a patient becomes pregnant during the study, the Investigator is to stop dosing with study drug(s) immediately.

A pregnancy is not considered to be an AE or SAE; however, it must be reported to the Sponsor using the Pregnancy Report Form within the same timelines as an SAE (Section 9.9). This applies to female patients as well as female partners of male patients.

A pregnancy should be followed through to outcome, whenever possible. Once the outcome of the pregnancy is known, the Pregnancy Outcome Report Form should be completed and reported to the Sponsor.

AEs or SAEs that occur during pregnancy will be assessed and processed according to the AE or SAE processes using the appropriate AE or SAE forms.

9.6 Adverse Events of Special Interest for MPDL3280A

The conditions listed below are of special interest and should be recorded within 24-48 hours of their occurrence.

Conditions suggestive of an autoimmune disorder:

- Pneumonitis;
- Hypoxia or Dyspnea \geq Grade 3;
- Colitis;
- Endocrinopathies: diabetes mellitus, pancreatitis, or adrenal insufficiency;
- Vasculitis;
- Hepatitis;
- Transaminitis: AST or ALT > 3 × ULN and bilirubin > 2 × ULN or AST/ALT > 10 × ULN;
- Systemic lupus erythematosus;
- Guillain barre syndrome;
- Myasthenia gravis;
- Pericardial effusion;
- Skin Reactions: vitiligo or pemphigoid;
- Events suggestive of hypersensitivity, cytokine release, influenza-like illness, SIRS, or infusion reaction syndromes.

9.7 Recording of AEs and SAEs

Any AE from the time the first dose of either study drug through 28 days after the last dose of study drug will be recorded on the AE eCRF. Study procedure-related AEs that occur after signing of the ICF and before first dose of either study drug will also be captured on the AE eCRF. Any other AE that occurs before first dose of study drug should be recorded on the Medical History eCRF. In order to avoid vague, ambiguous, or colloquial expressions, the AE should be recorded in standard medical terminology rather than the patient's own words. Whenever possible, the Investigator should combine signs and symptoms that constitute a single disease entity or syndrome. For example, fever, headache, and nasal discharge may be reported as coryza, if that is a reasonable diagnosis. The existence of an AE may be concluded from a

spontaneous report of the patient; from the physical examination; or from special tests such as the ECG, laboratory assessments, or other study-specified procedure.

Each AE is to be evaluated for duration, severity, seriousness, and causal relationship to each study drug. The action taken and the outcome must also be recorded.

SAEs that occur during the study or within 28 days after receiving the last dose of either study drug, whether or not related to rociletinib or MPDL3280A, must be immediately reported to the Sponsor/designee SAE contact (Section 9.9).

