1.4.2 Pharmacokinetics of MPDL3280A

On the basis of available preliminary PK data (0.03-20 mg/kg), MPDL3280A appeared to show linear PK at doses $\geq 1 \text{ mg/kg}$. For the 1-mg/kg and 20-mg/kg dose groups, the mean apparent CL and the mean Vss had a range of 3.20 to 4.44 mL/day/kg and 48.1 to 65.7 mL/kg, respectively, which is consistent with the expected profile of an IgG1 antibody in humans.

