7.7 Excluded Therapies Concurrent with MPDL3280A

The following therapies are excluded while patients are receiving MPDL3280A and for 10 weeks after the last dose of MPDL3280A.

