7.7.2 Immunomodulatory Agents

Patients are not allowed to receive immunostimulatory agents, including but not limited to IFN- α , IFN- γ , or IL-2. These agents, in combination with MPDL3280A, could potentially increase the risk for autoimmune conditions.

Patients should also not receive immunosuppressive medications, including but not limited to cyclophosphamide, azathioprine, methotrexate, and thalidomide. These agents could potentially alter the activity and the safety of MPDL3280A. Systemic corticosteroids and anti-TNF- α agents may attenuate potential beneficial immunologic effects of treatment with MPDL3280A but may be administered at the discretion of the treating physician after consultation with the Medical Monitor. If feasible, alternatives to these agents should be considered.

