8.2.2 End-of-Treatment Visit

Patients will be asked to return to the clinic for the EOT Visit 28 days (+7 days) after the last dose of study treatment, or before the patient initiates another anticancer agent (if sooner), to assess safety of the patients. Safety evaluation assessments for the EOT Visit are outlined in Table 1. All AEs (including SAEs and protocol-defined events of special interest), regardless of attribution, will be recorded until 28 days after the last dose of study treatment or until initiation of another anticancer therapy, whichever occurs first. Ongoing AEs considered related to study treatment and all SAEs, regardless of causality, will be followed until the event has resolved to baseline grade, the event is assessed by the Investigator as stable, new anticancer treatment is initiated, the patient is lost to follow up, the patient withdraws consent, or it is determined that the study treatment or participation is not the cause of the AE.

Tumor assessment scans do not need to be repeated if radiographic disease progression has been documented previously or the last scans were performed < 2 weeks before the last dose of study treatment or the patient had disease progression at the last scan. For patients who provide additional consent, an optional fresh tumor biopsy will be collected at the time of permanent treatment discontinuation due to disease progression (at the time the Investigator believes the patient is no longer deriving clinical benefit from study treatment, if treatment beyond radiographic disease progression is approved). This optional biopsy and associated blood samples scheduled for the EOT Visist (see Table 2) should occur as close as possible to the date of the decision to permanently discontinue study.

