11 PATIENT DISPOSITION

11.1 Permanent Discontinuation of Study Treatment

A patient must be discontinued from all study treatment if any of the following applies:

- Consent withdrawal at the patient's own request or at the request of their legally authorized representative;
- Clinical disease progression where the Investigator believes that the patient will not continue to benefit from study treatment (*Note:* patients will be permitted to continue study treatment after a radiographic progression [Appendix A: and Appendix B] if the benefit-risk ratio is judged to be favorable and continued treatment is approved by the Medical Monitor);
- Any event, adverse or otherwise, that, in the opinion of the Investigator, would pose an unacceptable safety risk to the patient;
- Any requirement for dose holds of rociletinib for more than 14 days or dose holds of MPDL3280A for more than 42 days, unless permission from the Sponsor's Medical Monitor for longer dose delay is granted;
- An intercurrent illness that, in the opinion of the Investigator, would affect assessments of the clinical status to a significant degree and requires discontinuation of therapy;
- A positive pregnancy test at any time during the study;
- Investigator decision.

In addition, the Sponsor may discontinue the study early for any of the reasons noted in Section 12.6.

The Sponsor (or designee) should be notified of all study terminations as soon as possible. The date and reason for cessation of PO rociletinib and/or IV MPDL3280A must be documented in the eCRF and source documents.

To the extent possible, EOT assessments should be performed for all patients who receive rociletinib and MPDL3280A. The EOT visit should occur 28 (\pm 7) days after the last dose of rociletinib and MPDL3280A. After stopping protocol-specified treatment, all patients will remain in the study and will be followed for safety (through 28 days after last dose; those with ongoing SAEs will be followed until either resolution or stabilization has been determined), for disease progression (every 8 \pm 1 weeks until disease progression), and for survival status and subsequent NSCLC therapies (at approximately quarterly intervals until death or Sponsor decision).

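### New immune-related events are recorded only to 28 days after the last dose of either drug, which can fall short of the 10 weeks for which the protocol restricts immunomodulators after MPDL3280A; separately, the EOT visit windows conflict

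*Combined protocol and SAP*

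**What the plan says.** **Recording of new events.** Section 9.7 records AEs from first dose "through 28 days after the last dose of study drug will be recorded on the AE eCRF". Section 9.1 gives the same limit, and Section 10.2.5.2 defines treatment-emergent AEs (TEAEs) up to 28 days after the last dose of either drug. Section 8.2.2 names the serious and special-interest classes expressly: "All AEs (including SAEs and protocol-defined events of special interest), regardless of attribution, will be recorded until 28 days after the last dose". There and in Table 1 (footnotes C and AA), recording ends earlier if another anticancer therapy begins.

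**After that window.** Section 9.8 provides for following events to resolution or stability, not for collecting new ones. The 12-weekly contacts in Section 8.3 gather survival and subsequent therapy. The visit 120 days after the last MPDL3280A dose is for PK and ATA samples (Synopsis, Table 2). The Follow Up column of Table 1 has no AE entry.

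**The longer horizon.** Section 7.7 states: "The following therapies are excluded while patients are receiving MPDL3280A and for 10 weeks after the last dose of MPDL3280A". For immunostimulatory agents, the reason in Section 7.7.2 is that in combination with MPDL3280A they "could potentially increase the risk for autoimmune conditions". Section 6.2 adds that there is no antidote and that stopping MPDL3280A may not help at once.

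**EOT visit.** Section 11.1: "The EOT visit should occur 28 (\pm 7) days". Section 8.2.2: "Patients will be asked to return to the clinic for the EOT Visit 28 days (+7 days) after the last dose of study treatment". Table 1 footnote C agrees with Section 8.2.2.

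**The concern.** The protocol manages other drugs around MPDL3280A for 10 weeks after the last infusion, but may stop looking for new immune-related events well before then. The conditions listed in Section 9.6 (pneumonitis, colitis, hepatitis and others) are the ones for which a late onset would matter. TEAEs are a Phase 1 primary endpoint, and the Clinical Safety Committee reviews safety in both phases. An event that starts after the window closes has no place on the AE form. Steroids given for it would leave no trace either, because Section 7 ends concomitant-medication recording at the same point. Section 10.2.5.2 plans listings of post-treatment AEs, but no section provides for collecting them.

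The EOT discrepancy is smaller. Under Section 11.1 the last scheduled safety visit can precede the end of the period it is meant to cover.

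**Working it through.** There is no plan figure to reproduce, because the plan gives no calculation on this point. The check sets the stated windows against each other, with a supporting look at drug persistence.

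**1. Recording window against the 10-week period.** Inputs: 28 days from the last dose of either drug (Sections 8.2.2, 9.7, 10.2.5.2); 10 weeks = 70 days from the last MPDL3280A dose (Section 7.7); MPDL3280A on Day 1 of each 21-day cycle with continuous rociletinib (Section 8.2). Let Day 0 be the last infusion and L the number of days for which rociletinib continues afterwards. Recording ends on Day 28 + L, so the uncovered part of the 70 days is max(0, 42 − L).

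| Situation | L | Recording ends | Uncovered |
|---|---|---|---|
| MPDL3280A is the last drug given | 0 | Day 28 | 42/70 = 60% |
| Rociletinib to the end of that cycle | 20 | Day 48 | 22/70 = 31% |
| Rociletinib alone for 42 days or more | ≥ 42 | Day 70 or later | 0 |

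Section 5.7.4 allows either drug to continue alone after the other is stopped for toxicity, so the first and last rows can both occur. Where Section 8.2.2 and Table 1 end recording at the start of new anticancer therapy, the uncovered part is larger.

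**2. Drug remaining.** Section 1.4.2 reports that "the mean apparent CL and the mean Vss had a range of 3.20 to 4.44 mL/day/kg and 48.1 to 65.7 mL/kg". With one-compartment elimination, half-life = ln 2 × Vss/CL and the fraction left at t days = exp(−CL/Vss × t). The pairing of CL with Vss is not given, so all four corners are shown.

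| Vss (mL/kg) | CL (mL/day/kg) | Half-life (days) | Day 28 | Day 48 | Day 70 |
|---|---|---|---|---|---|
| 48.1 | 4.44 | 7.5 | 7.5% | 1.2% | 0.2% |
| 48.1 | 3.20 | 10.4 | 15.5% | 4.1% | 0.95% |
| 65.7 | 4.44 | 10.3 | 15.1% | 3.9% | 0.88% |
| 65.7 | 3.20 | 14.2 | 25.6% | 9.7% | 3.3% |

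So about 8–26% remains at Day 28, about 1–10% at Day 48 and about 0.2–3.3% at Day 70.

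**3. Can existing contacts cover the gap?** The first follow-up contact is at 12 weeks ± 1 week: 84 ± 7 = Day 77–91 if counted from the last dose (Section 8.3 does not give the starting point), and later if counted from the EOT visit. The PK/ATA visit is at 120 ± 30 = Day 90–150 after the last MPDL3280A dose. Both come after Day 70, so either could ask about the whole period.

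**4. EOT window.** Section 11.1: 28 − 7 = 21 to 28 + 7 = 35. Section 8.2.2 and Table 1: 28 to 35. A Day 21 visit leaves 28 − 21 = 7 of the 28 days (25%) after the last scheduled AE assessment.

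**The case against.** The strongest objection concerns the clock. A reader might infer that any immune event from week 5 onward goes unrecorded, or that 60% of the period is always missed. The documents do not support that. The 28 days run from the last dose of either drug, and rociletinib is taken continuously, so a patient who stops both at the end of a cycle is covered to about Day 48. One who stays on rociletinib alone may be covered throughout. The 60% is the case in which MPDL3280A comes last.

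Second, Section 7.7 is a rule about other drugs. It also covers denosumab and immunosuppressants, for which the stated reason is altered activity and safety. The autoimmune wording concerns immunostimulants given with MPDL3280A. A reader might take the protocol to declare a 10-week autoimmune risk for MPDL3280A itself, but no section says so. The inference that it may still contribute is fair and remains an inference.

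Third, nothing shows a consequence. Residual drug is not an event rate, and the documents give no late-onset rate. Dose decisions rest on Cycle 1 DLTs, which this does not touch.

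Fourth, Section 9.7 requires reporting of "SAEs that occur during the study or within 28 days after receiving the last dose of either study drug", and Section 11.1 keeps patients in the study after treatment ends. Section 9.6 sets no end date for special-interest events. These could be read as a wider duty. That reading conflicts with the express limit in Section 8.2.2 and Table 1, and no later contact is set up to collect events. The ambiguity is a reason to clarify; it does not close the gap.

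Fifth, a Day 21 visit does not end recording. Section 11.1 itself requires safety follow-up through 28 days. That is right, and it makes the EOT point one of wording.

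**Conclusion.** The gap is real but depends on which drug stops last: 42 of 70 days (60%) if MPDL3280A does, about 22 of 70 (31%) if rociletinib runs to the end of the last cycle, and none if rociletinib alone continues for at least 42 days. An early start of new anticancer therapy widens it. Three assumptions stand behind this: that the 10-week restriction reflects a continuing contribution of MPDL3280A to autoimmune risk; that Section 8.2.2 and Table 1 govern where Section 9.7 could be read more widely; and, for the residual-drug figures only, one-compartment elimination. The finding rests on the stated windows, and the PK only supports it.

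Late immune-related events may be missed, so the safety profile may look more favourable than it is. A reader might go further and conclude that the combination does look safer than it is. Without a late-event rate, the documents cannot show that. The plan should be amended because the remedy is cheap; the point does not undermine the dose-finding design.

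The EOT discrepancy is a separate, minor contradiction between Section 11.1 and Section 8.2.2 with Table 1.

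**What to change.** 1. In Sections 8.2.2, 9.1 and 9.7 and in Table 1, provide for recording new Section 9.6 events and study-drug-related SAEs at least through the protocol's own 10-week period after the last MPDL3280A dose, including after new anticancer therapy starts. Ask about them at the existing 12-week contact and 120-day visit. State plainly whether the SAE wording in Section 9.7 is meant to reach beyond 28 days. Ten weeks is proposed because the documents contain it; they give no basis for a specific longer period for this purpose.
2. Keep the 28-day TEAE tables unchanged. Add one table of events with onset after each patient's own TEAE window closes, marking the start of any subsequent therapy. Starting from that point, and not from a fixed day after the last infusion, avoids counting the same event twice in patients who stayed on rociletinib.
3. Separately, reconcile the EOT window in Section 11.1 with Section 8.2.2 and Table 1, so that the last scheduled AE assessment is consistent with the 28-day recording window.

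Cost: amendment wording, a short CRF page and one table, with no new visits. Some late events will be confounded by the next therapy, and events elicited at a later contact depend on recall and records. Marking subsequent therapy lets the reader judge the confounding.

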9.7.1 Intensity of Adverse Events

The severity of the AE will be graded according to the NCI CTCAE v4.03 grading scale. For AEs not covered by NCI CTCAE v4.03, the severity will be characterized as mild, moderate, severe, or life-threatening according to the following definitions:

- Mild (Grade 1) events are usually transient and do not interfere with the patient's daily activities;
- Moderate (Grade 2) events introduce a low level of inconvenience or concern to the patient and may interfere with daily activities;
- Severe (Grade 3) events interrupt the patient's usual daily activities and hospitalization (or prolongation of hospitalization) may be required;
- Life-threatening (Grade 4) events require urgent intervention to prevent death.

